In the study, an observational clinical study strategy will be followed in routine spinal anesthesia applications. Applications will be made to the Erciyes University Ethics Committee. Patients will be informed before the procedure begins, and their written consent will be obtained. The study will be conducted from May 2025 to December 2025. ASA III and IV, preeclampsia, cardiorespiratory problems, pregnancy or pre-existing diabetes, intrauterine growth restriction, and fetal abnormalities, abruptio placentae, placenta previa, placenta accreta or percreta, pregnant women who are in an emergency situation and unwilling to participate, those with contraindications to spinal anesthesia, those weighing <50 kg or >110 kg, and those taller than 170 cm or shorter than 150 cm will not be included in the study. There was no pre-planning among the patients. The patient will undergo standard monitoring, including non-invasive blood pressure, ECG, and pulse oximetry, with baseline blood pressure and heart rate measurements recorded. Two 20-G intravenous cannulas will be inserted, and an IV balanced solution will be administered using these routes. Vertebral body length (VBL) measurements are determined by measuring from the midpoint of C7 to the Tuffier line. To test this hypothesis, a 0.5% heavy bupivacaine dose will be calculated as $0.2 \text{ mg} \times (\text{vertebral body length} = \text{distance between C7 and Tuffier's line}) \text{ cm}$. In our clinic, all three dose calculation systems are routinely used in spinal anesthesia for cesarean sections. As is routinely done, after skin infiltration with lidocaine, a 25-G short bevel Quincke spinal needle will be inserted into the L3-4 vertebral space while the patient is in a sitting position. After cerebrospinal fluid aspiration, the calculated dose of bupivacaine will be administered over 5 seconds. The patient and evaluator group assignments will be unknown. The data of 285 patients who underwent routine procedures will be examined, and the results will be separated based on the dose of bupivacaine administered to the pregnant woman. According to the results, the data is as follows: Patients in the VBU Group (thoracolumbar vertebral length between C7 and the Tuffier line) received $0.2 \text{ mg} \times \text{VBU cm}$ of 0.5% hyperbaric bupivacaine, while patients in the Height Group (calculated dose) received a volume of 0.5% hyperbaric bupivacaine based on a height-adjusted dose of 0.065 mg/cm height, calculated according to the patient's height. The AD Group (adjusted dosage) will receive intrathecal heavy bupivacaine (0.5%) as determined by Harten's dosage chart, adjusted for the patient's height and weight (Table 1) [11].

Postoperative analgesia will be performed bilaterally with a transverse abdominis plane block using 20 ml of 0.25% bupivacaine. The upper sensory level of anesthesia will be systematically assessed by measuring the loss of needle-prick sensation in the midclavicular line at 2-minute intervals. Additionally, the time to surgical incision, the sensory block level at the thirty-minute mark, the performance of the head-down tilt, the administration of additional analgesia, and the transition to general anesthesia will be recorded. Mean arterial blood pressure and heart rate will be recorded initially and then at 3-minute intervals starting 3 minutes after spinal injection and continuing until the end of the surgical procedures. The onset of nausea and vomiting will be systematically recorded along with the amount of ephedrine administered. A nurse present during delivery who is unaware of the patient's assigned group will assess the Apgar scores both 1 minute

Clinical Management

As per routine practice, patients will be immediately placed in the supine position with a 15-degree left lateral tilt. All patients will receive supplemental oxygen via a nasal cannula. Bradycardia (defined as a heart rate < 60 beats/min) will be treated with 0.5 mg of intravenous atropine. Hypotension, defined as a decrease in baseline systolic blood pressure of more than 30% or a systolic blood pressure below 90 mmHg, will be managed with 5 mg of intravenous ephedrine. In instances of dizziness, nausea, or vomiting, 5 mg of ephedrine will also be administered. Routine prophylaxis will be applied to prevent nausea and vomiting. Surgical incision will be permitted once the loss of pinprick sensation is confirmed bilaterally at the T6 dermatome. If patients experience discomfort during the procedure, a bolus of 0.5 mg/kg propofol and 0.25 mg/kg ketamine will be administered intravenously, consistent with routine practice. If these measures prove ineffective, the patient will be transitioned to general anesthesia and excluded from the study.

Following delivery, 100 IU of carbetocin will be administered as a uterotonic via graduated intravenous infusion. At the end of the procedure, 1000 mg of IV paracetamol will be administered for analgesic purposes. Supplemental postoperative analgesia will be provided via a bilateral transversus abdominis plane (TAP) block using 20 ml of 0.25% bupivacaine.

Monitoring and Data Collection

The upper sensory level of anesthesia will be systematically assessed every two minutes along the midclavicular line using the loss of pinprick sensation. Additionally, the time to surgical incision, the sensory block level at the 30-minute mark, the application of Trendelenburg positioning, the administration of supplemental analgesia, and any transitions to general anesthesia will be recorded. Mean arterial pressure (MAP) and heart rate will be recorded at baseline and every 3 minutes thereafter, beginning 3 minutes after the spinal injection and continuing until the end of the surgical procedure. The occurrence of nausea and vomiting, along with the total amount of ephedrine administered, will be systematically documented. An attending nurse, blinded to the patients' group assignments, will assess Apgar scores at both 1 and 5 minutes post-delivery.

Statistical Analysis

A pre-study power analysis was performed using G*Power (v3.1.9.7; Franz Faul, Universität Kiel, Germany) based on the primary hypothesis defined as the rate of hypotension in each group. Using data from retrospective studies and assuming an effect size of 0.30, it was calculated that at least 69 patients per group (207 total) were required for an ANOVA test. This calculation provides a study power of 0.95 with a significance level (α) of 0.05.

Data will be analyzed using Analysis of Variance (ANOVA), the Kruskal-Wallis test, and Fisher's exact test, as appropriate. Bonferroni corrections will be applied for multiple comparisons. A p-value < 0.05 will be considered statistically significant. All statistical analyses will be performed using JAMOV version 2.6.19 for Windows.

References:

- 3-Šklebar I, Bujas T, Habek D. Spinal anaesthesia-induced hypotension in obstetrics: Prevention and therapy. *Acta Clin Croat* 2019;58(Suppl 1):90-5.

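### Groups are to be formed from the administered dose, but they are defined by dosing formula, and the dose alone cannot identify the formula

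*Combined protocol and SAP*

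**What the plan says.** The study design paragraph of the combined protocol and SAP describes an observational study of 285 women treated in routine practice. It says "In our clinic, all three dose calculation systems are routinely used in spinal anesthesia for cesarean sections", and it gives no rule for which woman receives which. On forming the groups it says that "the results will be separated based on the dose of bupivacaine administered to the pregnant woman".

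The next sentences define the groups by formula:

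- **VBU Group:** "Patients in the VBU Group (thoracolumbar vertebral length between C7 and the Tuffier line) received" 0.2 mg per cm of that length.
- **Height Group:** a dose "based on a height-adjusted dose of 0.065 mg/cm height, calculated according to the patient's height".
- **AD Group:** a dose read from a published chart by height and weight (Table 1).

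Eligibility is limited by height ("those taller than 170 cm or shorter than 150 cm will not be included in the study") and by weight ("those weighing <50 kg or >110 kg" are excluded).

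Monitoring and Data Collection lists block level, time to incision, positioning, supplemental analgesia, conversion to general anesthesia, arterial pressure, heart rate, nausea and vomiting, ephedrine and Apgar scores. It does not list the formula used, the calculated dose or the delivered dose. Statistical Analysis bases the primary hypothesis on the hypotension rate in each group.

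**The concern.** The exposure is the formula, whereas the sorting rule uses milligrams. The two are interchangeable only if each dose points to one formula. If two formulas can produce the same dose, a woman's dose does not say which group she belongs to, and whoever prepares the data must decide by some unwritten rule.

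The hypotension comparison depends entirely on this label. With no randomisation list and no stated allocation rule, nothing else in the plan fixes the label. Sorting by milligrams would also make group membership depend on body size, because both printed formulas are multiples of a body measurement. A difference in hypotension between such groups could not be read as a difference between formulas.

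**Working it through.** The plan gives no figure for overlap or misclassification, so there is none to reproduce. The check uses the two formulas printed in the study design paragraph.

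**Inputs from the document.** Height formula: 0.065 mg per cm. Length formula: 0.2 mg per cm from C7 to Tuffier's line. Eligible height: 150 to 170 cm. Solution: 0.5%, which is 5 mg/mL.

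**Step 1: range of the height formula.**
- 0.065 × 150 = 9.75 mg; 9.75 / 5 = 1.95 mL
- 0.065 × 170 = 11.05 mg; 11.05 / 5 = 2.21 mL

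The whole Height Group therefore lies within 1.30 mg, or 0.26 mL.

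**Step 2: lengths that give the same doses.**
- 9.75 / 0.2 = 48.75 cm
- 11.05 / 0.2 = 55.25 cm

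Any woman dosed by length, with a length between these limits, has a dose that an eligible woman could receive under the height formula. On milligrams alone, only length doses outside 9.75 to 11.05 mg could be told apart from height doses. A VBU Group identified that way would hold only lengths below 48.75 cm or above 55.25 cm.

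**Step 3: two women, one dose.** A woman of 150 cm with a length of 52 cm, dosed by length, receives 0.2 × 52 = 10.4 mg. A woman of 160 cm, dosed by height, receives 0.065 × 160 = 10.4 mg. Dose alone cannot separate them. Their own measurements can, because the first woman's height dose would have been 9.75 mg.

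**Step 4: one woman, two formulas.** The doses are equal when 0.2 × length = 0.065 × height, so length = (0.065 / 0.2) × height = 0.325 × height. At 160 cm this is 52 cm, and both formulas give 10.4 mg. If her length is 1 cm from that value, the formulas differ by 0.2 mg, or 0.04 mL. For such women even their own measurements settle little.

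**Step 5: how often (assumptions only).** The document gives no distribution of vertebral length and no rounding practice. For illustration, assume height is normal with mean 160 and SD 5 cm, clipped to 150 to 170 cm; length is a fixed ratio of height plus a residual with SD 1.5 to 3.5 cm; and doses are rounded to 0.25 or 0.5 mg.

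| Assumed length/height ratio | Length doses inside 9.75–11.05 mg | Same dose from both formulas, 0.25 mg rounding | Same, 0.5 mg rounding |
|---|---|---|---|
| 0.30 | 36.0–39.4% | 1.3–7.4% | 4.6–14.8% |
| 0.325 | 60.2–86.6% | 14.0–31.5% | 27.2–54.4% |
| 0.35 | 37.3–39.5% | 1.3–7.4% | 5.2–15.1% |

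The second column is relevant if women are sorted on dose alone. The last two are relevant if each woman's measurements are used to work back to her formula. The spread shows that the frequency is unknown; it does not estimate it.

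**Step 6: the chart.** The values of Table 1 are not in the text available for this review, so overlap of the AD Group with the other two could not be checked.

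**The case against.** The strongest reply is that the sentence is loose wording for dosing method. The lines after it define the groups by formula, and the plan keeps patient, evaluator and the nurse scoring Apgar unaware of group. A label that is masked during care must exist during care. Also, height and weight are needed for eligibility and the measurement of length is described, so most women could be placed by working back from their own measurements.

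Much of this stands. The label may well exist, and back-calculation would narrow the ambiguity to women whose own formula doses coincide or nearly so. But the source of the label is not described, back-calculation is not planned, and length is not clearly measured in every woman. The only stated sorting rule still points to the dose.

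Three stronger readings are tempting, and the documents do not support them:

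- **That women are in fact misclassified.** The documents show that this is possible, not that it happens.
- **That the hypotension difference shrinks by a calculable amount.** The usual factor of 1 − 2m, for a fraction m swapped between two groups, assumes random swapping of women whose exposures differ. If the mislabelled women are those whose own formulas give the same dose, and they are otherwise comparable, symmetric swapping leaves the expected difference unchanged. If groups are formed purely by milligrams, the contrast is a different one and the factor does not apply. The documents give no group hypotension rates to apply it to.
- **That doses are rounded or altered at the bedside, perhaps by perceived risk.** The plan says that the calculated dose is given. Rounding and deviation are assumptions here.

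**Conclusion.** The concern holds as a defect in the written exposure definition. Groups defined by formula are to be sorted by dose, and the printed height and length formulas overlap over the whole Height Group range of 9.75 to 11.05 mg, with exact ties at length = 0.325 × height. This conclusion needs only the printed formulas, the height limits and the literal sorting rule. It does require that eligible women have lengths around 48.75 to 55.25 cm; the document gives no lengths, so this is an assumption.

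The number of women affected and the effect on the hypotension comparison cannot be determined from the documents. Nothing is established about overlap with the height-and-weight chart. The matter should still be settled before analysis, because the primary comparison rests on this label. If the formula is already charted for every woman, one sentence saying so and making it the group definition resolves the main point.

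**What to change.** Replace the sorting sentence in the study design paragraph with: *The formula used (length, height, or height-and-weight chart) is recorded before injection and defines the group, whatever volume is given.*

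Add to Monitoring and Data Collection, for every woman: height, weight, vertebral length, formula used, calculated dose and delivered dose. In Statistical Analysis, state that women are analysed by recorded formula, and that any difference between calculated and delivered dose is described by group.

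For women already treated, take the formula from the anesthetic record made at the time. Where it was not documented, report the woman as unclassified instead of inferring the formula from her dose.

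The cost is one tick-box, a few data fields and a few sentences of text. No dose and no part of clinical care changes.

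### Serial MAP and heart-rate readings have no stated longitudinal analysis: the listed tests ignore baseline, within-patient correlation and unequal series length, and the Bonferroni family is undefined

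*Combined protocol and SAP*

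**What the plan says.** The schedule for MAP and heart rate is given twice, consistently. The methods text before the Clinical Management heading has them "recorded initially and then at 3-minute intervals starting 3 minutes after spinal injection and continuing until the end of the surgical procedures". The Monitoring and Data Collection section repeats this schedule in slightly different words.

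The analysis is covered by three sentences in the Statistical Analysis section. The choice of test is given as "Data will be analyzed using Analysis of Variance (ANOVA), the Kruskal-Wallis test, and Fisher's exact test, as appropriate". On multiplicity, the section says only this: "Bonferroni corrections will be applied for multiple comparisons". The threshold is then set for every test alike: "A p-value < 0.05 will be considered statistically significant". None of the tests is tied to the serial readings. The section names no repeated-measures or mixed model, per-patient summary, baseline covariate, fixed time window or rule for series of different lengths. It does not say whether Bonferroni covers pairs of groups, time points, outcomes or some combination.

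Two other features matter. The study is described as observational, and the three groups are formed from the dosing method each patient received. The primary hypothesis concerns how often hypotension occurs, not serial MAP or heart rate.

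**The concern.** Readings on one patient every 3 minutes are correlated, and the series ends when her operation ends. A one-way ANOVA or Kruskal-Wallis test takes one independent value per patient. Applied to these data without further thought, it invites one of two analyses:

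- **A separate test at each time.** This gives many looks at the same variable. Unless the multiplicity correction spans the times, isolated time points will reach significance by chance. At late times the comparison is restricted to patients with long operations. Incision waits for the block to reach T6, so the length of the series may itself depend on how fast the block develops.
- **All readings pooled as if independent.** This overstates the sample size and badly understates the standard errors.

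In either case the recorded baseline is unused. In a non-randomised comparison nothing in the design makes baseline MAP and heart rate similar across the three groups, so a difference after injection could partly reflect a difference before it.

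**Working it through.** The plan gives no figure for this analysis. Its only calculation, "assuming an effect size of 0.30, it was calculated that at least 69 patients per group (207 total) were required for an ANOVA test", is for the hypotension comparison; whether that figure reproduces is a separate question and does not bear on this point.

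**Inputs from the document:** three groups; threshold 0.05; readings every 3 minutes; 285 patients to be examined, or 285/3 = 95 per group if equal (the split is not stated).

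**Assumptions:** 10 or 15 readings after injection (10 × 3 = 30 minutes, 15 × 3 = 45 minutes), because no operation length is given; within-patient correlation either AR(1) or exchangeable, at 0.7 or 0.9.

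**Step 1: upper reference.** If T readings were independent, the chance of at least one false positive would be 1 − 0.95^T: 1 − 0.95^10 = 40% and 1 − 0.95^15 = 54%. Positive correlation lowers this.

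**Step 2: correlated readings.** Null studies were simulated (3 groups of 95, 3,000 runs per setting) with a one-way ANOVA at each time. The table gives the chance of at least one significant time point for one variable. The last column uses 0.05/T (0.005 for 10 readings, 0.0033 for 15).

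| Readings | Correlation | Each time at 0.05 | Each time at 0.05/T |
|---|---|---|---|
| 10 | AR(1) 0.9 | 20.4% | 2.4% |
| 10 | AR(1) 0.7 | 30.6% | 4.4% |
| 10 | exchangeable 0.9 | 13.7% | 1.5% |
| 10 | exchangeable 0.7 | 23.2% | 3.5% |
| 15 | AR(1) 0.9 | 24.6% | 2.3% |
| 15 | AR(1) 0.7 | 41.4% | 3.4% |
| 15 | exchangeable 0.9 | 13.7% | 1.3% |
| 15 | exchangeable 0.7 | 27.4% | 3.3% |

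The Monte Carlo standard error is at most about √(0.414 × 0.586/3,000) = 0.9 percentage points. Repeat AR(1) runs with 69 or 95 per group gave 26–27% (0.9) and 41–42% (0.7) with 15 readings, and 19–20% and 29–31% with 10. Group size hardly matters.

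**Step 3: what Bonferroni does.** Limited to the three pairs of groups, it controls error within a time point but not across times, so the third column applies. Extended to all T times, the last column applies: below 5%, and as low as about 1–2% when correlation is strong.

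**Step 4: pooling.** One ANOVA on all readings treated as independent, with exchangeable correlation 0.3 to 0.7 and 10 to 20 readings, rejects a true null in about 44–81% of studies.

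**Step 5: baseline.** With baseline–follow-up correlation r, adjustment multiplies the residual variance by 1 − r². At r = 0.5 (an assumption) this is 1 − 0.25 = 0.75, a 25% reduction.

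**Step 6: check on the remedy.** If readings follow AR(1) but the model has only a random patient intercept, a null method-by-time interaction over 5 readings is rejected in about 8–9% of studies at strong autocorrelation (0.9), against the nominal 5%. The overall method effect stays near 5%. The remedy therefore needs a residual correlation structure.

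**The case against.** A reader might infer that the plan will test the groups at every time point and so will inflate false positives. The documents do not support that. No sentence says time-by-time tests will be run. The tests are listed for all data, to be chosen as suits, and the word ANOVA unqualified does not exclude a repeated-measures form. The readings could also be shown descriptively or reduced to one value per patient. The plan promises Bonferroni, and if that spans the time points the inflation disappears. These objections stand: inflation is conditional, not established.

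It is also fair to say that omitting baseline costs precision and balance rather than making a test invalid, that a per-patient summary would serve as well as a mixed model, and that the primary outcome is untouched. Hypotension is defined from systolic pressure, partly relative to baseline, and serial MAP and heart rate do not enter that definition.

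What survives is the gap itself. Bonferroni over time points does nothing about unused baseline or late readings that come only from longer operations, and it makes the tests conservative. Classical repeated-measures ANOVA, the most favourable reading, needs a complete series at common times, so it too requires a window or a rule for unequal lengths that the plan does not give.

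**Conclusion.** The point holds in conditional form. The plan collects correlated series of unequal length with a baseline, and lists tests that in ordinary form use none of that structure; the scope of the multiplicity correction is left open.

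If tests are run at each time and Bonferroni covers only group pairs, the chance of a spurious time point is about 26–42% per variable with 15 readings and about 19–31% with 10, under AR(1) correlation of 0.9 to 0.7. Exchangeable correlation at the same values gives about 14–27%. If Bonferroni covers the times, error is below 5% and the cost is power. The number of readings, the correlations and equal groups are assumptions. The absence of any provision for baseline, correlation and series length rests on the text alone.

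This should be put right before analysis, but it does not threaten the primary conclusion.

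**What to change.** In the Statistical Analysis section, for each of MAP and heart rate:

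- Prespecify one longitudinal model with dosing method, time, their interaction and the baseline value. Give it a within-patient residual correlation structure, for example AR(1) or unstructured, rather than a random intercept alone.
- Restrict it to a fixed early window that all patients reach, set before the data are compared by group.
- Report one overall method effect, averaged over that window, as differences between methods with 95% confidence intervals. Apply Bonferroni to the three pairwise method contrasts and say that this is the family.
- Show readings after the window descriptively, with the number of patients still contributing at each time.

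An acceptable simpler alternative is an ANCOVA, adjusted for baseline, of one summary per patient over the same window, such as the lowest or mean value.

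The cost is a few sentences of wording and a little more analysis work. No new data are needed, because baseline and the 3-minute readings are already collected. Adjustment for the baseline value does not make the three groups comparable in other respects.

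### Women converted to general anesthesia after the spinal dose are excluded, so the dosing methods are compared only among women not converted

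*Combined protocol and SAP*

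**What the plan says.** The opening description of the design forms three groups (VBU, Height and AD) according to how the dose was calculated: "the results will be separated based on the dose of bupivacaine administered to the pregnant woman". On numbers it says: "The data of 285 patients who underwent routine procedures will be examined".

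Clinical Management sets out two steps when the block is not comfortable. First: "If patients experience discomfort during the procedure, a bolus of 0.5 mg/kg propofol and 0.25 mg/kg ketamine will be administered intravenously". Then: "If these measures prove ineffective, the patient will be transitioned to general anesthesia and excluded from the study".

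Monitoring and Data Collection lists, among the items to be captured, "the administration of supplemental analgesia, and any transitions to general anesthesia will be recorded". The paragraph before Clinical Management contains much the same list.

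Statistical Analysis gives a sample size "based on the primary hypothesis defined as the rate of hypotension in each group" and names ANOVA, Kruskal-Wallis and Fisher's exact tests. It does not define an analysis population, say whether excluded women are replaced, plan a sensitivity analysis, or say how conversions are to be reported by group.

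**The concern.** The exclusion is not an eligibility rule. By the time it applies, the woman has had her intrathecal dose and belongs to a group. Its trigger is discomfort that supplementation did not control, and an inadequate block, hence the dose, is a plausible cause. If the three methods differ in how often this happens, the rule removes a different fraction and a different kind of patient from each group.

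Two things are at stake. The primary hypotension rates would describe women not converted rather than women dosed by each method. And a dosing method has to be judged on both sides, hypotension and adequacy of the block. If the converted women drop out of the comparison, the most severe failures on the second side may not appear beside the first.

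The groups are formed from routine care, so their comparability is already uncertain. A selection made after the dose adds to that uncertainty and is avoidable.

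**Working it through.** **Inputs.** From the documents: three groups, 285 patients planned, at least 69 per group (207 in total) required, hypotension rate as the primary hypothesis. Not in the documents, so assumed: equal groups (285/3 = 95), that the 285 counts dosed women, every conversion rate, and every hypotension rate. The plan gives no figure for conversion, so there is none to reproduce on this point.

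**The plan's sample size, for context.** A balanced one-way ANOVA with three groups, "assuming an effect size of 0.30" (read as Cohen's f), α = 0.05 and power 0.95 needs 59 per group, 177 in total. The stated 207 gives power 0.977. The stated figure is therefore not reproduced, but it errs on the safe side and nothing below depends on it.

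**Step 1: bound on one group's rate.** With m of n dosed women excluded,

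rate(all dosed) − rate(retained) = (m/n) × (rate among excluded − rate among retained).

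The bracket lies between −1 and +1, so the shift is at most m/n in either direction.

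| Converted, m | n = 95 | n = 69 |
|---|---|---|
| 1 | 1.1 points | 1.4 points |
| 2 | 2.1 | 2.9 |
| 5 | 5.3 | 7.2 |
| 10 | 10.5 | 14.5 |

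A difference between two groups can move by at most the sum of their shares. With 5 and 1 converted out of 95 each, that is 6/95 = 6.3 points.

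**Step 2: direction.** Assume a hypotension rate of 40% among all dosed women in a group. With share e excluded and rate r among the excluded, the analysed rate is (0.40 − e·r)/(1 − e).

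| e | r = 0 | r = 0.8 |
|---|---|---|
| 1% | 40.4% | 39.6% |
| 5% | 42.1% | 37.9% |
| 10% | 44.4% | 35.6% |

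Excluding women with little hypotension raises the group's rate; excluding women with much hypotension lowers it. The two columns are illustrations, not limits.

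**Step 3: effect on the comparison.** Assume 50% hypotension among retained women in both of two groups, and 10% among converted women. The retained-only difference is 0.

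- Conversion 1% vs 5%: 0.99 × 0.50 + 0.01 × 0.10 = 49.6%, and 0.95 × 0.50 + 0.05 × 0.10 = 48.0%. The all-dosed difference is 1.6 points.
- Conversion 2% vs 10%: 49.2% vs 46.0%, a difference of 3.2 points.
- Equal conversion: difference 0.
- Conversion 1% vs 5%, but 90% hypotension among converted women: 0.495 + 0.009 = 50.4%, and 0.475 + 0.045 = 52.0%. The difference is again 1.6 points, in the opposite direction.

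Balanced conversion cancels in these examples because the gap between converted and retained women is the same in both groups.

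**Step 4: the passages side by side.** Clinical Management takes the converted woman out of the study; Monitoring and Data Collection says "any transitions to general anesthesia will be recorded". These fit together only if conversions are counted for women who are otherwise left out of the analysis, and the plan does not say so.

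**The case against.** The strongest case for leaving the rule alone is that its effect may be negligible. If conversion is rare or similar across methods, the hypotension comparison barely moves: one converted woman in 95 shifts a rate by at most 1.1 points. Power is not threatened either, with 285 planned against 207 required. This stands as a statement about size. It does not justify the rule, because neither rarity nor balance is known in advance and nothing in the plan would show whether they held.

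Three stronger readings are tempting, and the documents do not support them.

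- A reader might infer that the methods are compared only in women in whom the dose worked. That goes too far. Women whose discomfort is controlled with propofol and ketamine stay in, and their supplemental analgesia is recorded, so less severe block inadequacy remains visible.
- A reader might infer that conversion is lost as an outcome, or is zero by construction. The plan says conversions are recorded, and they could be tabulated outside the main comparison. What is missing is a statement that they will be, by group.
- A reader might infer that the rule flatters a method that gives too little drug. Step 2 shows the reverse if converted women had little hypotension: their removal raises that method's rate. The direction is unknown.

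It is also fair to say that the plan does not attribute conversion to underdosing. The trigger is discomfort, and incision waits for bilateral loss of pinprick sensation at T6. The dose is a plausible cause, not a documented one, and plausibility is enough to make the exclusion unsafe. The rule also does not say how a woman who never reaches T6 is handled.

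**Conclusion.** The concern holds in this form. The plan removes women after the group-defining dose because of an event that the dose can plausibly cause, lists that same event as recorded data, and has no analysis set or by-group reporting to repair this. Applied as written, the rule can shift a group's hypotension rate up or down by at most the share of that group excluded, and it can leave the most severe block failures out of the comparison of methods.

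The per-patient bound of about 1.1 points rests on an equal split of 285 dosed women. All the other percentages rest on assumed rates. The actual bias cannot be calculated from the documents and may be small. The case for change is that the rule decides who is counted in the primary comparison and is easy to remove before analysis.

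**What to change.** In Clinical Management, end the sentence at the transition to general anesthesia and delete the words that exclude the patient. The clinical rule on when to convert is not in question and stays as it is. In Statistical Analysis, add:

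- **Analysis set.** Every woman who received the intrathecal dose is analysed in the group of her dosing method, including women converted at any point.
- **Hypotension in converted women.** Apply the plan's definition to readings up to induction of general anesthesia.
- **Block adequacy.** Report supplemental analgesia and conversion to general anesthesia by group, next to hypotension.
- **Sensitivity analysis.** An analysis without converted women may be shown, but only in that role.

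Counting converted women as hypotension events is not advised as the remedy, because it mixes block failure with low blood pressure and answers a different question.

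The cost is one deletion, one definition and slightly more analysis work, with no extra patients or procedures, since supplemental analgesia and conversion are already recorded. The drawback is shorter blood-pressure follow-up in converted women, which should be stated in the report. The change does not make groups formed in routine care comparable at baseline; it only removes a selection made after the dose.
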